4.2 Aim: descriptive tables/plots for additional variables

Analysis: we will describe or plot the distributions of additional variables at baseline, hearing aid fit, or 3 month visit as appropriate by assigned treatment. For GHABP, the two unaided (baseline) questions and the one aided (3-month) question (averaged and standardized) will only include patients who answered "yes" to the first question (if the scenario happens). These will be reported across the 4 standard scenarios.

Table 2: Distributions of Clinical Variables by Assigned Treatment

	Unilateral (N=XXX)	Bilateral (N=XXX)
GHABP Unaided: How much difficulty do you have in this situation?		
N	XXX	XXX
Missing	XXX	XXX
Mean (SD)	XXX (XXX)	XXX (XXX)
Median	XXX	XXX
Q1, Q3	XXX, XXX	XXX, XXX
Range	XXX - XXX	XXX - XXX
GHABP Unaided: How much does any difficulty in this situation worry, annoy or upset you?		
N	XXX	XXX
Missing	XXX	XXX
Mean (SD)	XXX (XXX)	XXX (XXX)
Median	XXX	XXX
Q1, Q3	XXX, XXX	XXX, XXX
Range	XXX - XXX	XXX - XXX

GHABP Aided: In this situation, with your hearing aid, how much does any difficulty in this situation worry, annoy, or upset you?

N	XXX	XXX
Missing	XXX	XXX
Mean (SD)	XXX (XXX)	XXX (XXX)
Median	XXX	XXX
Q1, Q3	XXX, XXX	XXX, XXX
Range	XXX - XXX	XXX - XXX

ECHO Global Score (Baseline)

N	XXX	XXX
Missing	XXX	XXX
Mean (SD)	XXX (XXX)	XXX (XXX)
Median	XXX	XXX
Q1, Q3	XXX, XXX	XXX, XXX
Range	XXX - XXX	XXX - XXX

ECHO Positive Effect Subscale (Baseline)

N	XXX	XXX
Missing	XXX	XXX
Mean (SD)	XXX (XXX)	XXX (XXX)
Median	XXX	XXX
Q1, Q3	XXX, XXX	XXX, XXX
Range	XXX - XXX	XXX - XXX

ECHO Service Cost Subscale (Baseline)

N	XXX	XXX
Missing	XXX	XXX
Mean (SD)	XXX (XXX)	XXX (XXX)
Median	XXX	XXX
Q1, Q3	XXX, XXX	XXX, XXX
Range	XXX - XXX	XXX - XXX

ECHO Negative Features Subscale (Baseline)

N	XXX	XXX
Missing	XXX	XXX
Mean (SD)	XXX (XXX)	XXX (XXX)
Median	XXX	XXX
Q1, Q3	XXX, XXX	XXX, XXX
Range	XXX - XXX	XXX - XXX

ECHO Personal Image Subscale (Baseline)

N	XXX	XXX
Missing	XXX	XXX
Mean (SD)	XXX (XXX)	XXX (XXX)
Median	XXX	XXX
Q1, Q3	XXX, XXX	XXX, XXX
Range	XXX - XXX	XXX - XXX

SADL Positive Effect Subscale (3 Months)

N	XXX	XXX
Missing	XXX	XXX
Mean (SD)	XXX (XXX)	XXX (XXX)
Median	XXX	XXX
Q1, Q3	XXX, XXX	XXX, XXX
Range	XXX - XXX	XXX - XXX

SADL Service Cost Subscale (3 Months)

N	XXX	XXX
Missing	XXX	XXX
Mean (SD)	XXX (XXX)	XXX (XXX)
Median	XXX	XXX
Q1, Q3	XXX, XXX	XXX, XXX
Range	XXX - XXX	XXX - XXX

SADL Negative Features**Subscale (3 Months)**

N	XXX	XXX
Missing	XXX	XXX
Mean (SD)	XXX (XXX)	XXX (XXX)
Median	XXX	XXX
Q1, Q3	XXX, XXX	XXX, XXX
Range	XXX - XXX	XXX - XXX

SADL Personal Image Subscale (3 Months)

N	XXX	XXX
Missing	XXX	XXX
Mean (SD)	XXX (XXX)	XXX (XXX)
Median	XXX	XXX
Q1, Q3	XXX, XXX	XXX, XXX
Range	XXX - XXX	XXX - XXX

HHI-E Total Score (Baseline)

N	XXX	XXX
Missing	XXX	XXX
Mean (SD)	XXX (XXX)	XXX (XXX)
Median	XXX	XXX
Q1, Q3	XXX, XXX	XXX, XXX
Range	XXX - XXX	XXX - XXX

HHI-E Total Score (3-Month)

N	XXX	XXX
Missing	XXX	XXX
Mean (SD)	XXX (XXX)	XXX (XXX)
Median	XXX	XXX
Q1, Q3	XXX, XXX	XXX, XXX
Range	XXX - XXX	XXX - XXX

HHI-E Situational Subscale**(Baseline)**

N	XXX	XXX
Missing	XXX	XXX

Mean (SD)	XXX (XXX)	XXX (XXX)
Median	XXX	XXX
Q1, Q3	XXX, XXX	XXX, XXX
Range	XXX - XXX	XXX - XXX
HHI-E Situational Subscale (3-Month)		
N	XXX	XXX
Missing	XXX	XXX
Mean (SD)	XXX (XXX)	XXX (XXX)
Median	XXX	XXX
Q1, Q3	XXX, XXX	XXX, XXX
Range	XXX - XXX	XXX - XXX
HHI-E Emotional Subscale (Baseline)		
N	XXX	XXX
Missing	XXX	XXX
Mean (SD)	XXX (XXX)	XXX (XXX)
Median	XXX	XXX
Q1, Q3	XXX, XXX	XXX, XXX
Range	XXX - XXX	XXX - XXX
HHI-E Emotional Subscale (3-Month)		
N	XXX	XXX
Missing	XXX	XXX
Mean (SD)	XXX (XXX)	XXX (XXX)
Median	XXX	XXX
Q1, Q3	XXX, XXX	XXX, XXX
Range	XXX - XXX	XXX - XXX
Tinnitus Presence (Baseline)		
No	XXX (XXX%)	XXX (XXX%)
Yes	XXX (XXX%)	XXX (XXX%)
Missing	XXX (XXX%)	XXX (XXX%)
TFI Overall Score (Baseline)		
N	XXX	XXX
Not Applicable (Answered No to Presence)	XXX	XXX
Missing	XXX	XXX
Mean (SD)	XXX (XXX)	XXX (XXX)
Median	XXX	XXX
Q1, Q3	XXX, XXX	XXX, XXX
Range	XXX - XXX	XXX - XXX
SSQ Overall Score (Baseline)		
N	XXX	XXX
Missing	XXX	XXX
Mean (SD)	XXX (XXX)	XXX (XXX)
Median	XXX	XXX
Q1, Q3	XXX, XXX	XXX, XXX
Range	XXX - XXX	XXX - XXX
SSQ Overall Score (3-Month)		
N	XXX	XXX

Missing	XXX	XXX
Mean (SD)	XXX (XXX)	XXX (XXX)
Median	XXX	XXX
Q1, Q3	XXX, XXX	XXX, XXX
Range	XXX - XXX	XXX - XXX

SSQ Speech/Hearing Subscale

(Baseline)

N	XXX	XXX
Missing	XXX	XXX
Mean (SD)	XXX (XXX)	XXX (XXX)
Median	XXX	XXX
Q1, Q3	XXX, XXX	XXX, XXX
Range	XXX - XXX	XXX - XXX

SSQ Speech/Hearing Subscale

(3-Month)

N	XXX	XXX
Missing	XXX	XXX
Mean (SD)	XXX (XXX)	XXX (XXX)
Median	XXX	XXX
Q1, Q3	XXX, XXX	XXX, XXX
Range	XXX - XXX	XXX - XXX

SSQ Spatial/Hearing Subscale

(Baseline)

N	XXX	XXX
Missing	XXX	XXX
Mean (SD)	XXX (XXX)	XXX (XXX)
Median	XXX	XXX
Q1, Q3	XXX, XXX	XXX, XXX
Range	XXX - XXX	XXX - XXX

SSQ Spatial/Hearing Subscale (3-

Month)

N	XXX	XXX
Missing	XXX	XXX
Mean (SD)	XXX (XXX)	XXX (XXX)
Median	XXX	XXX
Q1, Q3	XXX, XXX	XXX, XXX
Range	XXX - XXX	XXX - XXX

SSQ Qualities of Hearing

Subscale (Baseline)

N	XXX	XXX
Missing	XXX	XXX
Mean (SD)	XXX (XXX)	XXX (XXX)
Median	XXX	XXX
Q1, Q3	XXX, XXX	XXX, XXX
Range	XXX - XXX	XXX - XXX

SSQ Qualities of Hearing

Subscale (3-Month)

N	XXX	XXX
Missing	XXX	XXX
Mean (SD)	XXX (XXX)	XXX (XXX)

Median	XXX	XXX
Q1, Q3	XXX, XXX	XXX, XXX
Range	XXX - XXX	XXX - XXX
Binaural Loudness Summation:		
Right (Baseline)		
N	XXX	XXX
Missing	XXX	XXX
Mean (SD)	XXX (XXX)	XXX (XXX)
Median	XXX	XXX
Q1, Q3	XXX, XXX	XXX, XXX
Range	XXX - XXX	XXX - XXX
Binaural Loudness Summation:		
Left (Baseline)		
N	XXX	XXX
Missing	XXX	XXX
Mean (SD)	XXX (XXX)	XXX (XXX)
Median	XXX	XXX
Q1, Q3	XXX, XXX	XXX, XXX
Range	XXX - XXX	XXX - XXX
Binaural Loudness Summation:		
Both (Baseline)		
N	XXX	XXX
Missing	XXX	XXX
Mean (SD)	XXX (XXX)	XXX (XXX)
Median	XXX	XXX
Q1, Q3	XXX, XXX	XXX, XXX
Range	XXX - XXX	XXX - XXX
Dichotic Digits: Right Ear Directed (Baseline)		
N	XXX	XXX
Missing	XXX	XXX
Mean (SD)	XXX (XXX)	XXX (XXX)
Median	XXX	XXX
Q1, Q3	XXX, XXX	XXX, XXX
Range	XXX - XXX	XXX - XXX
Dichotic Digits: Left Ear Directed (Baseline)		
N	XXX	XXX
Missing	XXX	XXX
Mean (SD)	XXX (XXX)	XXX (XXX)
Median	XXX	XXX
Q1, Q3	XXX, XXX	XXX, XXX
Range	XXX - XXX	XXX - XXX
Dichotic Digits: Free Recall Both (Baseline)		
N	XXX	XXX
Missing	XXX	XXX
Mean (SD)	XXX (XXX)	XXX (XXX)
Median	XXX	XXX
Q1, Q3	XXX, XXX	XXX, XXX

Range	XXX - XXX	XXX - XXX
Dichotic Digits: Free Recall Right (Baseline)		
N	XXX	XXX
Missing	XXX	XXX
Mean (SD)	XXX (XXX)	XXX (XXX)
Median	XXX	XXX
Q1, Q3	XXX, XXX	XXX, XXX
Range	XXX - XXX	XXX - XXX
Dichotic Digits: Free Recall Left (Baseline)		
N	XXX	XXX
Missing	XXX	XXX
Mean (SD)	XXX (XXX)	XXX (XXX)
Median	XXX	XXX
Q1, Q3	XXX, XXX	XXX, XXX
Range	XXX - XXX	XXX - XXX
Speech and Noise Test: 0 Degrees (Co-located) Score (Baseline)		
N	XXX	XXX
Missing	XXX	XXX
Mean (SD)	XXX (XXX)	XXX (XXX)
Median	XXX	XXX
Q1, Q3	XXX, XXX	XXX, XXX
Range	XXX - XXX	XXX - XXX
Speech and Noise Test: 0 Degrees (Co-located) Score (3-Month)		
N	XXX	XXX
Missing	XXX	XXX
Mean (SD)	XXX (XXX)	XXX (XXX)
Median	XXX	XXX
Q1, Q3	XXX, XXX	XXX, XXX
Range	XXX - XXX	XXX - XXX
Speech and Noise Test: Speech Left, Noise Right Score (Baseline)		
N	XXX	XXX
Missing	XXX	XXX
Mean (SD)	XXX (XXX)	XXX (XXX)
Median	XXX	XXX
Q1, Q3	XXX, XXX	XXX, XXX
Range	XXX - XXX	XXX - XXX
Speech and Noise Test: Speech Left, Noise Right Score (3-Month)		
N	XXX	XXX
Missing	XXX	XXX
Mean (SD)	XXX (XXX)	XXX (XXX)

Median	XXX	XXX
Q1, Q3	XXX, XXX	XXX, XXX
Range	XXX - XXX	XXX - XXX
Speech and Noise Test: Speech Left, Noise Right Change Score		
N	XXX	XXX
Missing	XXX	XXX
Mean (SD)	XXX (XXX)	XXX (XXX)
Median	XXX	XXX
Q1, Q3	XXX, XXX	XXX, XXX
Range	XXX - XXX	XXX - XXX
Speech and Noise Test: Noise Left, Speech Right Score (Baseline)		
N	XXX	XXX
Missing	XXX	XXX
Mean (SD)	XXX (XXX)	XXX (XXX)
Median	XXX	XXX
Q1, Q3	XXX, XXX	XXX, XXX
Range	XXX - XXX	XXX - XXX
Speech and Noise Test: Noise Left, Speech Right Score (3-Month)		
N	XXX	XXX
Missing	XXX	XXX
Mean (SD)	XXX (XXX)	XXX (XXX)
Median	XXX	XXX
Q1, Q3	XXX, XXX	XXX, XXX
Range	XXX - XXX	XXX - XXX
Speech and Noise Test: Noise Left, Speech Right Change Score		
N	XXX	XXX
Missing	XXX	XXX
Mean (SD)	XXX (XXX)	XXX (XXX)
Median	XXX	XXX
Q1, Q3	XXX, XXX	XXX, XXX
Range	XXX - XXX	XXX - XXX
Auditory Working Memory - Recognition Score (Baseline)		
N	XXX	XXX
Missing	XXX	XXX
Mean (SD)	XXX (XXX)	XXX (XXX)
Median	XXX	XXX
Q1, Q3	XXX, XXX	XXX, XXX
Range	XXX - XXX	XXX - XXX
Auditory Working Memory - Recognition Score (3-Month)		
N	XXX	XXX
Missing	XXX	XXX
Mean (SD)	XXX (XXX)	XXX (XXX)

Median	XXX	XXX
Q1, Q3	XXX, XXX	XXX, XXX
Range	XXX - XXX	XXX - XXX
Auditory Working Memory - Recall Score (Baseline)		
N	XXX	XXX
Missing	XXX	XXX
Mean (SD)	XXX (XXX)	XXX (XXX)
Median	XXX	XXX
Q1, Q3	XXX, XXX	XXX, XXX
Range	XXX - XXX	XXX - XXX
Auditory Working Memory - Recall Score (3-Month)		
N	XXX	XXX
Missing	XXX	XXX
Mean (SD)	XXX (XXX)	XXX (XXX)
Median	XXX	XXX
Q1, Q3	XXX, XXX	XXX, XXX
Range	XXX - XXX	XXX - XXX
Auditory Working Memory - Judgement Score (Baseline)		
N	XXX	XXX
Missing	XXX	XXX
Mean (SD)	XXX (XXX)	XXX (XXX)
Median	XXX	XXX
Q1, Q3	XXX, XXX	XXX, XXX
Range	XXX - XXX	XXX - XXX
Auditory Working Memory - Judgement Score (3-Month)		
N	XXX	XXX
Missing	XXX	XXX
Mean (SD)	XXX (XXX)	XXX (XXX)
Median	XXX	XXX
Q1, Q3	XXX, XXX	XXX, XXX
Range	XXX - XXX	XXX - XXX

We will plot the average absolute difference between target and output at each frequency for each ear by assigned hearing aid configuration for both the hearing aid fit and 3-month visits (with visits either grouped together in the same plot or plotted separately). We will also do this for the average difference between MPO and UCL at each frequency.

5 Future Plans

There are additional items we may wish to explore in the future, at which point a new SAP will be developed. Ideas include looking at:

- Additional GHABP measures
- EMA surveys
- Mask questions

- Additional hearing aid hours of use
- Unscheduled visits

Statistical Analysis Plan (SAP) – Secondary (6-Month) Outcomes and Descriptives

Project: Evaluation of Unilateral vs Bilateral Hearing Aids for the Treatment of Age-related Hearing Loss

IRB Number: Pro00106077

Investigator(s): [name], AuD, PhD

Biostatisticians: [name], [name], [name], [name]

Original Creation Date: 01.07.2025

Version Date: 01.07.2025

Investigator Agreement

- All statistical analyses included in an abstract or manuscript should reflect the work of the biostatistician(s) listed on this SAP. No changes or additional analyses should be made to the results or findings without discussing with the project biostatistician(s).
- All biostatisticians on this SAP should be given sufficient time to review the full presentation, abstract, manuscript, or grant and be included as co-authors on any abstract or manuscript resulting from the analyses.
- If substantial additional analysis is necessary or the aims of the project change, a new SAP will need to be developed.
- Publications resulting from this SAP are supported in part by the Duke CTSA and must cite grant number UL1TR002553 and be submitted to PubMed Central.
- I have reviewed the SAP and understand that any changes must be documented.

Acknowledged by: Click or tap here to enter text.

Date: Click or tap to enter a date.

Activity Log

Acronyms	APHAB	Abbreviated Profile of Hearing Aid Benefit
	IOI-HA	International Outcomes Inventory for Hearing Aids
	SADL	Satisfaction with Amplification in Daily Life
	SSQ	Speech Spatial Qualities
	HHIE	Hearing Handicap Inventory for Elderly

1 Study Overview

Background/Introduction: The overall goal of the project is to determine the benefit of unilateral or bilateral hearing aid fittings in adults with mild-to-moderate age-related hearing loss. This will address the lack of high-quality evidence supporting bilateral hearing aids over unilateral hearing aids. This project will use a randomized controlled trial with two treatment arms: a bilateral hearing aid fitting group and a unilateral hearing aid fitting group.

1.1 Aims for Secondary Outcomes

- Compare all outcomes between the two arms (bilateral hearing aid and unilateral hearing aid) at 6 months. *The primary hypothesis is that bilateral hearing aids are superior to the unilateral hearing aids with respect to the overall patient-reported benefit.*
 - Descriptive tables for additional clinical variables at 6-months by assigned treatment
 - Plots of APHAB Global score and change from baseline by assigned treatment
- Compare all outcomes at 6 months by final configuration choice
- Compare all outcomes at 6 months by switching status relative to baseline

2 Study Population

2.1 Inclusion Criteria

- 50+ years of age
- Mild to moderate, symmetrical SNHL (symmetrical: < 20 dB between ears on average from 500-4000 Hz)
- Open-mindedness to unilateral or bilateral amplification
- No prior hearing aid experience
- Adequate literacy to complete questionnaires
- Willing to purchase study-specific hearing aid(s)

2.2 Exclusion Criteria

- Concerns for middle ear pathology
- Concerns for retrocochlear pathology
- Severe tinnitus as the reason for seeking amplification
- Co-morbid condition that would interfere with study (e.g., dementia, blindness, neurologic pathology)
- History of fluctuating hearing loss

2.3 Data Acquisition

Fill in all relevant information:

Study design	Randomized controlled trial with 2 arms (bilateral hearing aid, unilateral hearing aid) Note: Randomization was stratified by clinical site.
Data source/how the data were collected	Screening information pulled from EHR data Baseline surveys captured via in-person interview and recorded in REDCap
Contact information for team member responsible for data collection/acquisition	All data access is through [REDACTED] [REDACTED]. Questions on data validity will go to PI: [name] ([contact])
Date or version (if downloaded, provide date)	10.28.2024
Data transfer method and date	Direct data extraction from REDCap
Where dataset is stored	REDCap Extracted data and analytic datasets are stored on a secure drive in the CRU folder: \\duhs-vclin-nc1\dusom_biostats_fs\Data\BiostatsCore\CRU\Head and Neck\[name]\PCORI_Pro00106077\Data pulls

--	--

Notes: Additional variable details for all variables can be found in the “PCORI Variable Details” Excel file. Scoring details can be found in “PCORI Scoring 20240923”.

3 Outcomes, Exposures, and Additional Variables of Interest

3.1 Outcome(s)

Outcome	Description	Variables and Source	Specifications
APHAB Change Score	Difference in aided APHAB scores at month 6 and unaided scores at baseline	aphab_global_change_6m (constructed in analytic script)	
Scale score – will need to calculate global communication scores at baseline (unaided) and 3 months (aided), subtract (3 months – baseline)
 
A lower score on APHAB is better.
 
Rescore variables and multiply by 100
 
 • 1 = 0.99 • 2 = 0.87 • 3 = 0.75 • 4 = 0.50 • 5 = 0.25 • 6 = 0.12 • 7 = 0.01 
Reverse score questions 1, 9, 11, 16, 19, 21
 
Global score: mean of variables in the EC, BN, RV subscale scores (excludes questions 3, 8, 13, 17, 20, 22)
 
Note: APHAB has 4 subscales and a global communication scale. The study is powered based on the benefit score on the global communication scale (August 2019 draft – APHAB SD of 25 with different levels of Cohen’s D).

APHAB change score – binary, 6 months	Responders vs non-responders for primary APHAB outcome	
Decrease of 25 units: aphab_responder25_6m
 
Decrease of 15 units: aphab_responder15_6m
 
(Constructed in analytic script)
	
Patients with a decrease of at least 25 units (or 15 units for the sensitivity analysis) on the APHAB scale at month 6 will be considered “responders.”
 
Patients not returning or who do not have a score at 6

			
months will be considered “non-responders.” Patients with a baseline score < 25 (or < 15) are ineligible (missing).
 
Binary (25 unit decrease):
 
 • Missing if baseline score <25 • 1 if aphab_global_change_6m <=-25 • 0 else 
Binary (15 unit decrease);
 
 • Missing if baseline score <15 • 1 if aphab_global_change_6m <=-15 • 0 else
APHAB – 4 subscales	EC, BN, RV, AV scales at 6 months and change score relative to baseline	6-month variables: aphab_ec_6m aphab_bn_6m aphab_rv_6m aphab_av_6m	
Rescore variables and multiply by 100
 
 • 1 = 0.99 • 2 = 0.87 • 3 = 0.75 • 4 = 0.50 • 5 = 0.25 • 6 = 0.12 • 7 = 0.01 
Reverse score questions 1, 9, 11, 16, 19, 21
 
EC: mean of questions 4, 10, 12, 14, 15, 23
 
BN: mean of questions 1, 6, 7, 16, 19, 24
 
RV: mean of questions 2, 5, 9, 11, 18, 21
 
AV: mean of questions 3, 8, 13, 17, 20, 22

IOI-HA	Total score Note: this is measured only at 3 and 6 months	ioiha_total_6m	
Total score: sum responses to questions 1-7 (should be on a range between 1-5).
 
Item 8 is self-perceived hearing difficulty used for normative purposes (currently not used as part of total score)

			
This is initially coded as 0 to 4 in REDCap – changed to 1-5
 
Currently, we're treating IOI-HA total score as continuous, but this may need to be treated as ordinal.
 
Higher scores are better

SADL	
Note: this is measured only at 3 and 6 months.
 
Note: the “sister” questionnaire at baseline is ECHO
	
Global score: sadl_global_6m
 
Positive effect subscale: sadl_positive_effect_6m
 
Service cost subscale: sadl_service_cost_6m
 
Negative features subscale: sadl_negative_features_6m
 
Personal image subscale: sadl_personal_image_6m
	
Questions 1 – 15 are used. This is scored from 1-7 (or reversed for questions 2, 4, 7, 13).
 
There are 4 subscales: Positive Effect, Service & Cost, Negative Features, Personal Image. For each subscale, the average score is calculated.
 
For the global score, this is the mean of the scores for all items (excluding questions 11 and 14 if applicable).
 
Higher scores are better (higher satisfaction).
 
See PCORI Scoring file for more details

SSQ	Note: this is measured at baseline, 3 months, and 6 months.	
Change score (constructed in analytic script): ssq_overall_change_6m
 
Baseline:
 
Overall score: ssq_overall_base
 
Speech/hearing subscale: ssq_speech_hearing_base
 
Spatial/hearing subscale: ssq_spatial_hearing_base
 
Qualities of hearing subscale: ssq_qualities_of_hearing_base
 
6-Months:
 
Overall score: ssq_overall_6m
	
3 subscales: Speech is questions 1 – 14 (corresponds to the “pt1” variables). Spatial is 17 questions (corresponds to the “pt2” variables). Qualities is 18 questions (correspond to the “pt3” variables).
 
Overall score: mean of the items.
 
For instances where people mark NA and a value, if the value is 50, set as NA. If a value other than 50, use that value.
 
We will also create a change score as the difference in the overall score between 6 months and baseline (6 months – baseline)

		
Speech/hearing subscale: ssq_speech_hearing_6m
 
Spatial/hearing subscale: ssq_spatial_hearing_6m
 
Qualities of hearing subscale: ssq_qualities_of_hearing_6m
	Higher scores are better
HHI-E	Note: this is measured at baseline, 3 months, and 6 months	
Change score (constructed in analytic script): hhie_total_change_6m
 
Baseline:
 
Total score: hhie_total_base
 
Social/Situational subscale: hhie_situational_base
 
Emotional subscale: hhie_emotional_base
 
6-Months:
 
Total score: hhie_total_6m
 
Social/Situational subscale: hhie_situational_6m
 
Emotional subscale: hhie_emotional_6m
	
Yes = 4 points, Sometimes = 2 points, and No = 0 points.
 
Total scale score = sum of all 25 items
 
Social/Situational subscale: questions 1, 3, 6, 8, 10, 11 13, 15, 16, 19, 21, 23
 
Emotional subscale: questions 2, 4, 5, 7, 9, 12, 14, 17, 18, 20, 22, 24, 25
 
We will also create a change score as the difference in the total scale score between 6 months and baseline (6 months – baseline)
 
Lower scores are better

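### The formula for the 6-month APHAB change score names the 3-month visit and so contradicts the rest of its own row

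*SAP*

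**What the plan says.** The SAP for secondary 6-month outcomes defines its APHAB change score in one row of the table in section 3.1, and the cells of that row disagree about the visit.

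- The Description cell says "Difference in aided APHAB scores at month 6 and unaided scores at baseline".
- The Variables cell gives "aphab_global_change_6m (constructed in analytic script".
- The Specifications cell, the only one that states the arithmetic, says "calculate global communication scores at baseline (unaided) and 3 months (aided), subtract (3 months", followed by minus baseline.

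The next row builds the two responder outcomes on this variable. The 25-unit version is coded 1 when "aphab_global_change_6m <=-25", and the 15-unit version works the same way. In words, the responder definition refers to a decrease "on the APHAB scale at month 6 will be considered" a response.

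The other two change scores in the same table name the later visit. SSQ uses the difference in the "overall score between 6 months and baseline (6 months – baseline", and HHI-E the difference in the "total scale score between 6 months and baseline (6 months – baseline".

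**The concern.** A Specifications cell is what a programmer codes from, and this one names the wrong visit for an outcome that the SAP says is derived in the script. No other cell in the SAP gives a formula for this variable.

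The choice of visit matters here because of the design. Under the protocol's Month 3 Visit (section 4), questionnaires are completed after three months on the assigned configuration, and participants may then keep, change or return their aids. The 6-month assessment is meant to describe the configuration they chose. Section 4.4 of the 6-month SAP cites participants' tendency to switch at 3 months as a reason for dropping the longitudinal models. A 3-month score under a 6-month label would therefore describe another time and, for those who switched at month 3, another configuration.

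**Working it through.** The plan gives no figure to reproduce here. The check compares the text, then works out what the literal formula would compute.

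**1. Which visit does each place name?**

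| Place in the 6-month SAP | Visit |
|---|---|
| 3.1, APHAB change, Specifications | month 3 |
| 3.1, APHAB change, Description | month 6 |
| 3.1, APHAB change, variable name | month 6 |
| 3.1, responder definitions | month 6 |
| 3.1, SSQ and HHI-E change rules | month 6 |
| 1.1, aim; 4.1, population and Table 1 title | month 6 |

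Only the Specifications cell names month 3. Its sentence is word for word that of the primary SAP, section 3.1, where it defines `aphab_change`, the 3-month outcome, and is correct. The natural explanation is text copied from the 3-month SAP and not updated. The 6-month SAP has the same creation and version date (01.07.2025) and an empty activity log, so this is current text.

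**2. What would the literal formula compute?** Write G0, G3 and G6 for a participant's APHAB global score at baseline, month 3 and month 6.

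- Intended: G6 − G0
- Literal: G3 − G0, the same quantity as `aphab_change` in the primary SAP
- Error: (G3 − G0) − (G6 − G0) = G3 − G6

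Baseline cancels, so the error is the movement between months 3 and 6. Lower scores are better. A participant who worsened after month 3 (G6 > G3) would be credited with too much benefit, and one who improved with too little. In a comparison of two groups, the error is the difference between the groups in mean G3 − G6. The documents give no value for this, so its size cannot be stated.

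**3. Responders.** A participant is misclassified whenever G3 − G0 and G6 − G0 fall on opposite sides of −25 (or −15). The definition also counts anyone without a 6-month score as a non-responder. The literal coding would give such a person their 3-month status, unless the restriction in section 4.1 to patients with 6-month scores removes them first.

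**4. How many tests?** Table 1 (section 4.1) tests seven outcomes: APHAB global change, two APHAB responder outcomes, SADL, HHI-E change, IOI-HA and SSQ change. Three depend on this variable. Sections 4.2 and 4.3 repeat the table by final choice (Table 3) and by switching status (Table 4).

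- Affected: 3 outcomes × 3 tables = 9 tests
- Total: 7 outcomes × 3 tables = 21 tests

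The boxplots of the global change score in section 4.1 are also affected.

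**5. Effect in Tables 3 and 4.** Take a participant assigned one aid who moved to two at month 3. G3 was recorded on one aid. Under the literal formula, Table 3 would enter that score in the bilateral column, and Table 4 would enter it as a switcher's 6-month outcome.

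**6. What is untouched?** The 6-month APHAB global total and 6-month subscale scores in Table 2, the other four outcomes in Table 1, and the primary 3-month analysis do not use this formula.

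**The case against.** The strongest reply is that this is a copying slip whose intended meaning is not in doubt. The description, variable name, responder text, aim, population and parallel rows all point to month 6, and a programmer would have to override them to go wrong. Variable and scoring details are also held in separate files that the SAP cites and that are not available here, and these may state the rule correctly. Planned outputs offer a cross-check: the global score averages the EC, BN and RV items, so with complete items the global change must equal the mean of the three subscale changes in Table 2, and 3-month values would generally not reconcile. The 6-month outcomes are secondary, and the protocol (section 4, Month 6 Visit) describes them as exploratory.

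All of this stands. It makes the error less likely to reach the results and limits its importance. It does not make the formula right, and nothing in the plan requires the cross-check.

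A reader might also infer three stronger things that the documents do not support.

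- *That 3-month data were actually analysed as 6-month data.* The script is not shown, and the row contradicts itself; it does not consistently specify month 3.
- *That the 6-month analysis would duplicate the 3-month one.* The primary SAP (sections 4.3 and 4.6) uses linear and logistic regression with site, in 3-month completers and in all eligible randomized patients respectively. The 6-month SAP (section 4.1) uses t-tests or Kruskal-Wallis tests and chi-square tests, without site, in patients with 6-month scores. Tables 3 and 4 have no counterpart in the primary SAP.
- *That the results would show benefit to be fully maintained.* Section 4.4 abandons the longitudinal models, and no test of month 3 against month 6 is planned. The supportable statement is that benefit could appear maintained to someone reading the two sets of results together.

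**Conclusion.** The point holds as an internal contradiction in a derivation rule. The only formula given for the 6-month APHAB change score uses the wrong visit by the SAP's own account. If followed, it would affect 9 of the 21 tests in Tables 1, 3 and 4, together with the change-score boxplots. The consequence is most serious in Tables 3 and 4, because scores from before a month-3 switch would be attributed to the configuration chosen afterwards.

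The consequence is conditional on the script having followed the Specifications cell. The numerical size of any error depends on how scores moved between months 3 and 6, which the documents do not give. The primary conclusion of the trial does not depend on this variable. The point is worth correcting because it fixes which visit is analysed, and that should not be left to inference.

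**What to change.** Replace the Specifications text with: APHAB global score at 6 months (aided) minus APHAB global score at baseline (unaided), that is `aphab_global_6m − aphab_global_base`. Both variables are already named in section 3.1 of the Hearing Aid Choice and Switching SAP. Record the correction in the activity log.

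Then confirm that the script builds `aphab_global_change_6m` and both responder variables from the 6-month items. A quick test is to check, in participants with complete items, that the global change equals the mean of the EC, BN and RV 6-month changes.

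The cost is one line of SAP text and one check of the script. The SAP's deadline for these analyses was January 24, 2025, so they may already have been run. If the script proves to have used month 3, the nine tests and the change-score boxplots need rerunning; if not, only the text changes. No new data are needed and the design is unaffected.
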